#### 4.2.2 Biologic Endpoints

4.2.2.1 A 3-mm punch biopsy of a non-indicator KS lesion will be performed at baseline and between Days 22 and 28 of cycle 1. Biopsies will be fixed in formalin and studied by immunohistochemistry (IHC) for expression of the following: VEGF, VEGFR-2, VEGFR-3, phospho-Akt, KSHV LANA, orf59, p53 and HIF-1 $\alpha$ . Tumor cell proliferation will be assessed by Ki-67 staining. Change in the intensity or distribution of a particular marker will be evaluated. Ki 67 staining will be quantified as a percentage of tumor cells. All other immunohistochemical staining will be described with a score (0, 1+, 2+) and a description of the distribution of the signal (endothelial cells, spindle cells, infiltrating lymphocytes, etc.). Depending on the results of these assays, other potential immunohistochemical markers characteristic for KS may also be measured. A detailed protocol is provided in Appendix XIII.

Evaluation by IHC of the effects of PTC299 on KSHV LANA and orf 59 is based on the hypothesis that either VEGF depletion directly, or VEGF inhibition-induced hypoxia indirectly, may induce KSHV lytic gene expression. Because reduction of VEGF production is expected to reduce capillary-dependent oxygen flow to the tumor, this will, in turn, induce hypoxia. Hypoxia causes p53-dependent apoptosis but also, via HIF-1 $\alpha$ , induces VEGF. HIF-1 $\alpha$  and the cellular response to hypoxia are modulated by KSHV. Hence, p53, HIF-1 $\alpha$ , and some of their representative targets will be characterized by IHC as secondary biological endpoints.

4.2.2.2 A separate 3-mm biopsy of a non-indicator KS lesion will be performed at baseline and again between Days 22 and 28 of cycle 1 to assess viral gene expression within tumor at the messenger RNA level. Real-time QPCR based profiling of KSHV transcription will be used to test the hypothesis that depletion of VEGF directly or indirectly through the induction of hypoxia may lead to changes in KSHV transcription. This has previously been observed in laboratory studies.[134-137] A detailed protocol is provided in Appendix V.

4.2.2.3 Using the same biopsies as described in Section 4.2.2.2, Real-time QPCR based profiling will be used to test the hypothesis that depletion of VEGF directly, or indirectly through the induction of hypoxia, may lead to changes in cellular gene transcription.

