## 11.2 Statistical Analysis Plan

Descriptive statistics will be used to summarize the demographic and baseline characteristics of the study population. Subjects who do not complete the required observations will be described and evaluated separately, as necessary. Reasons for study discontinuation and date of withdrawal from study will be described

The binomial proportion and its 95% confidence interval will be used to estimate the objective (complete + partial) response rate as defined in Section 8.0. With 12 patients at the maximally treated dose, the response rate can be estimated with a 95% confidence interval with width no greater than  $\pm 28.3\%$ .

The effects of PTC299 on serum and plasma VEGF, VEGFR and cytokine profiles will be evaluated by comparing the Day 28 value with the pre-treatment value, and the Day 28 value with the lowest value obtained subsequent to Day 28. These changes will be evaluated using the paired t-test, or if the data are not normally distributed, the Wilcoxon signed rank test. Comparisons between dose levels with respect to these changes will be evaluated using ANOVA or the Kruskal-Wallis test if the data are not normally distributed.

Comparisons of on-treatment values with the pre-treatment baseline value, and with the corresponding baseline value within each cycle will be performed using paired t-tests. If the distribution of the data deviates substantially from normality, the analysis will be performed on log-transformed data. Differences in change from baseline among dose levels will be analyzed by means of ANOVA (including a test for linear dose response); if a significant effect is observed, individual comparisons among dose levels will be performed with t-tests. The pattern of responses across doses will be considered in interpreting the logical validity of the results. Results will be presented in tabular and graphic form, as appropriate.

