Immunohistochemistry (IHC) will be used to determine expression of the following: VEGF, VEGFR-2, VEGFR-3, phospho-Akt, KSHV LANA, orf59, p53 and HIF-1 $\alpha$ . We will count the number of positive cells per HPF for a total of 10 fields per section and derive an index value. We will consider a 50% change from baseline in the index value for the aforementioned markers a biological response. For each measure (VEGF, VEGFR-2, VEGFR-3, phospho-Akt, KSHV LANA, orf59, p53 and HIF-1 $\alpha$ ), we will estimate the proportion of patients who demonstrate a 50% change between baseline and on treatment (between day 22 and day 28) value. The exact binomial 95% confidence interval will be derived for each measure.

To evaluate the effects of PTC299 on tumor cell proliferation, the change in immunohistochemistry of Ki67 from the pre-treatment to the post-treatment biopsy will be tested using the Wilcoxon sign test to determine if the change is less than zero, suggesting a decrease. To evaluate the drug's effects on circulating concentrations of angiogenic factors and cytokines, HIV and KSHV loads, and T-lymphocyte subsets, changes in these levels from pre-treatment to indicated sampling times will be tested by repeated-measures ANOVA, single and multivariate analysis.

For each subject, study drug administration will be described in terms of the actual doses administered and the proportion of drug actually delivered relative to the amount that should have been delivered. The total number of cycles administered; the median (range) of cycles administered; dose modifications, dose delays, and dose omissions; and reasons for deviations from planned therapy will be described by starting dose level. The type and timing of use of concomitant drugs will also be described.

AEs and laboratory abnormalities will be summarized by type and severity grade. First-cycle DLTs, adverse events leading to death or to discontinuation from treatment, and serious adverse events will be considered with special attention.

Pharmacokinetic parameters will be calculated using the actual sample collection times. Pharmacokinetic variables will be calculated from the plasma concentration data using standard compartmental and noncompartmental methods, as appropriate for the data. Variables of interest may include  $T_{max}$ ,  $C_{max}$ ,  $C_{24h}$ ,  $AUC_{0-24}$ , and  $t_{1/2}$ . Plasma concentrations and PK parameter results will be presented in tabular and graphic form by dose level and

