## APPENDIX XIII: DETECTION OF VIRAL AND HOST PROTEIN EXPRESSION IN KS TISSUES

### Description of the Assay

Changes in protein expression are a fundamental hallmark of cancer progression and an invaluable tool of cancer staging. In case of KS, KSHV/HHV-8 has been identified as the etiological agent and this assay is designed to identify KSHV proteins and cellular proteins that might change in response to therapy. The previous assay used PCR to look at changes in mRNA level. This assay uses histochemistry to look at changes in protein expression.

Biopsies will be fixed in formalin and studied by immunohistochemistry (IHC) for expression of the following: VEGF, VEGFR-2, VEGFR-3, phospho- Akt, KSHV LANA, orf59, p53 and HIF-1a. Tumor cell proliferation will be assessed by Ki-67 staining. Change in the intensity or distribution of a particular marker will be evaluated.

This assay is a research test only and will not be used to make clinical decisions.

Biopsies should be obtained by standard punch technique, using a THREE (3) mm punch from non-indicator KS lesions. Tumor biopsies should be completely within the margins of the lesions.

The first biopsy should be obtained at baseline (see section 4.2.2.1)

A second biopsy should be obtained between days 22 and 28 of cycle 1.

Each specimen should then be immersed in 1.5 ml formalin and stored at room temperature until shipment and labeled as follows:

Samples must be labeled with the bar-coded labels provided. Each sample should be labeled with the following information:

- **Protocol #:** “AMC-059”
- **Nine (9) Digit Subject ID:** “XXX-XXX-XXX”
- **Date of Sample Collection**
- **Specimen Type** “KS tumor” or “normal skin”
- **Specimen Purpose:** “IHC”

The samples should be shipped by overnight courier on wet ice within two (2) days to:

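### Section 11.2 counts an undirected 50% change in each of eight IHC markers as a biological response, so the single reported rate cannot separate falls in VEGF from rises

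*Combined protocol and SAP*

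**What the plan says.** The IHC paragraph of Section 11.2 covers VEGF, VEGFR-2, VEGFR-3, phospho-Akt, KSHV LANA, orf59, p53 and HIF-1α. Six of these are named in secondary objective 2.2.5; LANA and orf59 are not.

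- Measurement: "We will count the number of positive cells per HPF for a total of 10 fields per section and derive an index value".
- Response rule: "We will consider a 50% change from baseline in the index value for the aforementioned markers a biological response".
- Summary: for each marker, "we will estimate the proportion of patients who demonstrate a 50% change between baseline and on treatment", the on-treatment biopsy being taken between Days 22 and 28. Each proportion gets an exact binomial 95% interval.

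No direction is attached to any of the eight markers. The next paragraph does give one for Ki-67, where the test asks whether the change is below zero.

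Section 4.2.2.1 supplies the biology. On the drug's intended action it says: "Because reduction of VEGF production is expected to reduce capillary-dependent oxygen flow to the tumor". On what may follow it says: "Hypoxia causes p53-dependent apoptosis but also, via HIF-1"α, VEGF is induced.

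The same section describes the readout for every stain except Ki-67 differently: "All other immunohistochemical staining will be described with a score (0, 1+, 2+) and a description of the distribution of the signal". Appendix XIII, cited there as the detailed protocol, says: "Change in the intensity or distribution of a particular marker will be evaluated". Neither mentions a cell count, an index or a 50% cut-off.

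**The concern.** The drug is meant to lower VEGF production, and the paired biopsies are the tissue-level look at whether it does. Section 4.2.2.1 describes a route to lower VEGF and a route back up. A response rate that adds the two outcomes cannot tell suppression of the target from its induction.

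This proportion is the only analysis in Section 11.2 written specifically for these eight markers. If it is reported as written, a reader who sees a VEGF biological response rate will probably take it as evidence of suppression, and the figure does not carry that meaning. At stake is the interpretation of a secondary, descriptive endpoint.

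**Working it through.** The plan states no sample size, expected rate or precision for the IHC proportions, so there is no planned figure to reproduce. The check is a comparison of the text followed by an illustration.

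**Text.** Three places bear on direction:
1. Section 11.2, IHC paragraph: a 50% change, either way, for all eight markers.
2. Section 11.2, Ki-67 sentence: direction stated (decrease).
3. Section 4.2.2.1: reduced VEGF production is presupposed, and VEGF induction through hypoxia is described.

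No passage ties a direction to the eight-marker response rule.

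**What pooling hides.** If k subjects meet the undirected rule, the number with a fall can be any integer from 0 to k. That is true of any two-sided count. It matters here because the protocol describes a mechanism for each direction in the same marker.

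**Illustration.** Inputs:
- n = 15, the total planned at the Stage 3 expansion dose in Section 3.3.1. It is an assumption that all 15 have evaluable paired biopsies; the documents do not say how many will.
- k = 6 pooled responders, chosen only for illustration.
- Exact (Clopper-Pearson) 95% limits for x out of n: lower = 0.025 quantile of Beta(x, n − x + 1), upper = 0.975 quantile of Beta(x + 1, n − x). The lower limit is 0 when x = 0.

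Results for n = 15:

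| Count | Proportion | Exact 95% CI |
|---|---|---|
| 6/15 (pooled) | 40% | 16.3% to 67.7% |
| 5/15 | 33% | 11.8% to 61.6% |
| 1/15 | 7% | 0.2% to 31.9% |
| 0/15 | 0% | 0% to 21.8% |

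Five falls with one rise, and one fall with five rises, both give the first row. Split by direction, the first pattern is 5/15 falls and 1/15 rises, and the second is the reverse. At the extremes, the pooled 6/15 is compatible with anything from 0/15 to 6/15 falls.

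**Other values of n.** The same split with two other subject numbers from Section 11.1:

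| n | Pooled 6/n | 5/n | 1/n |
|---|---|---|---|
| 12 (minimum at the Stage 3 dose) | 50% (21.1% to 78.9%) | 42% (15.2% to 72.3%) | 8% (0.2% to 38.5%) |
| 38 (maximum evaluable) | 16% (6.0% to 31.3%) | 13% (4.4% to 28.1%) | 3% (0.1% to 13.8%) |

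These are examples. The documents give other counts too (8 in Stage 2, 11 for the first Simon stage, up to 21 in Stage 3, 44 in all), and none is stated as the number with paired IHC biopsies. The ambiguity is present at every n.

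**The case against.** The strongest reply is that the undirected rule is deliberate. Objective 2.2.5 is to describe effects, Section 4.2.2.1 and Appendix XIII also speak of change without a sign, and the protocol has mechanisms running both ways. The authors gave a direction for Ki-67 when they wanted one. This is plausible and cannot be excluded. It does not rescue the single rate, because a screen for change in either direction is better served by two rates, and the pooled count is their sum.

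A second reply is that direction is not lost. This stands. Both index values are recorded, so the sign can be recovered at analysis, and the score in Section 4.2.2.1 would also show it. The general statement "Comparisons of on-treatment values with the pre-treatment baseline value, and with the corresponding baseline value within each cycle will be performed using paired t-tests" might cover IHC, but it names no endpoint, and its within-cycle baseline fits a single on-treatment biopsy poorly. None of these is tied to the biological response rate itself.

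A reader might also infer three stronger points:
- **That the index cannot be formed, because the assay sections describe a score.** The documents do not support this. Nothing there excludes counting, and both readings can come from the same slide. It is a wording mismatch to align.
- **That the rule is biased because a 50% fall is a 2-fold change (ratio 0.5) and a 50% rise only 1.5-fold (ratio 1.5).** The thresholds are symmetric on the percent scale the plan chose. Preferring a fold scale is a matter of taste, and splitting by direction leaves the inequality in place.
- **That a stated share of responders would be assay noise.** That requires a variability figure, and the documents give none.

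**Conclusion.** The point holds in a limited form. As written, the VEGF biological response rate treats a fall and a rise as the same outcome, and so cannot show which occurred. Under the assumption of 15 paired biopsies and six pooled responders, a reported 40% could correspond to a VEGF decrease rate of 33% or of 7%, or to any count of decreases from none to six.

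The conclusion rests on a literal reading of Section 11.2; the authors may intend to look at direction informally. A reader might infer that the trial's main findings are compromised. The documents do not support that: no dose decision, stopping rule or sample size depends on this proportion, and the MTD and objective-response conclusions are unaffected. The missing index formula and the absent rule for a zero baseline, where percent change is undefined, are small gaps in detail and do not carry the finding. The change is still worth making, because it is nearly free and is best settled before the biopsy data are analysed.

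**What to change.** In Section 11.2, for each of the eight markers, report the proportion with at least a 50% decrease and the proportion with at least a 50% increase separately, each with its exact 95% interval. State that for VEGF the decrease is the response of interest. The pooled proportion may stay alongside.

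As minor housekeeping, state in Section 4.2.2.1 and Appendix XIII that positive cells per field over 10 fields are recorded alongside the score. In Section 11.2, define the index (for example, the mean count over the 10 fields) and say how a zero baseline is handled (for example, listed separately and left out of the percent-change proportion).

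The cost is wording and one more table row per marker, eight in all. No extra biopsies or staining are needed, since the counting is already planned. The downside is that each separate proportion can be no larger than the pooled one and will usually be smaller.

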## APPENDIX V: DETECTION OF VIRAL AND HOST RNA LEVELS IN KS TISSUES

### Description of the Assay

Changes in gene expression are a fundamental hallmark of cancer progression and invaluable tool of cancer staging. In case of KS, KSHV/HHV-8 has been identified as the etiological agent and this assay is designed to identify KSHV genes that might change in response to therapy. We will use reverse-transcription (RT) coupled to amplification using polymerase chain reaction (PCR) to measure the RNA levels of all KSHV/HHV-8 mRNAs in tumor biopsies. Secondly, we will use a custom-made array for cellular targets, which we presume to be regulated by VEGF, hypoxia or both. This assay is a research test only and will not be used to make clinical decisions.

We will use a targeted array of 96 mRNAs that were previously shown to be involved in angiogenesis, endothelial cell remodeling or hypoxic responses. This array is based upon PAHS-024 (SuperArray, Inc.). It may be modified based upon literature review but most likely will include the following growth factors and receptors: ANGPT1, ANGPT2, ANPEP, ECGF1, EREG, FGF1, FGF2, FIGF, FLT1, JAG1, KDR, LAMA5, NRP1, NRP2, PGF, PLXDC1, STAB1, VEGFA, VEGFC. Adhesion molecules: ANGPTL3, BAI1, COL4A3, IL8, LAMA5, NRP1, NRP2, STAB1. Proteases, inhibitors and other matrix proteins: ANGPTL4, PECAM1, PF4, PROK2, SERPINF1, TNFAIP2. Transcription factors and others: HAND2, SPHK1. Cytokines and chemokines: CCL11, CCL2, CXCL1, CXCL10, CXCL3, CXCL5, CXCL6, CXCL9, IFNA1, IFNB1, IFNG, IL1B, IL6, MDK, TNF. Other growth factors and receptors: EDG1, EFNA1, EFNA3, EFNB2, EGF, EPHB4, FGFR3, HGF, IGF1, ITGB3, PDGFA, TEK, TGFA, TGFB1, TGFB2, TGFBRI. Adhesion molecules: CCL11, CCL2, CDH5, COL18A1, EDG1, ENG, ITGAV, ITGB3, THBS1, THBS2. Proteases, inhibitors and other matrix proteins: LECT1, LEP, MMP2, MMP9, PLAU, PLG, TIMP1, TIMP2, TIMP3. Transcription factors and others: AKT1, HIF1A, HPSE, ID1, ID3, NOTCH4, PTGS1.

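### The 50%-change rule for eight IHC markers is undefined at a zero baseline and unreliable at low cell counts, which matters most for orf59, where a rise is hypothesised

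*Combined protocol and SAP*

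**What the plan says.** Section 11.2 sets out the readout for VEGF, VEGFR-2, VEGFR-3, phospho-Akt, KSHV LANA, orf59, p53 and HIF-1α: "We will count the number of positive cells per HPF for a total of 10 fields per section and derive an index value". The responder rule follows: "We will consider a 50% change from baseline in the index value for the aforementioned markers a biological response". The planned estimate is per marker: "we will estimate the proportion of patients who demonstrate a 50% change between baseline and on treatment (between day 22 and day 28) value". Its precision is given by an interval: "The exact binomial 95% confidence interval will be derived for each measure". The section gives no direction of change, no minimum baseline count, no rule for a zero baseline and no formula for the index. Ki-67 is analysed separately, as a paired change.

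Section 4.2.2.1 gives the reason for staining LANA and orf59: VEGF depletion, or the hypoxia that follows from it, "may induce KSHV lytic gene expression". The same section describes the readout differently. Ki-67 is a percentage of tumour cells, and for the rest: "All other immunohistochemical staining will be described with a score (0, 1+, 2"+), together with the distribution of the signal.

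**The concern.** A percentage change needs a baseline that is above zero and large enough to be stable. The rule guarantees neither. A subject with no orf59-positive cells before treatment and many afterwards would be the clearest support for the induction hypothesis, yet the plan does not say whether that subject is a responder, a non-responder or not evaluable. The numerator and denominator of the binomial proportion are therefore not fixed in advance.

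With only a few positive cells at baseline, one or two cells more or fewer satisfy the rule. A proportion inflated in this way would be reported with an exact interval that allows for the number of subjects but not for misclassification of each subject. The same rule governs the six count-index markers that objective 2.2.5 does name.

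**Working it through.** **Figure to reproduce.** Section 11.2 states no sample size, error rate, baseline count or expected proportion for this endpoint, so there is none. The number 12 used below is the minimum at the top dose in section 11.1. The nearby half-width of 28.3% in section 11.2 concerns objective response and reproduces as 1.96 × √(0.25/12) = 0.283.

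**Zero baseline.** Change/baseline has a zero denominator. This needs no model.

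**Low baseline: assumptions.** Let B and T be the total positive cells over 10 fields at baseline and on treatment. Assume that they are independent Poisson counts with the same mean L, so there is no drug effect. An index proportional to the total, such as a mean per field, gives the same ratios. The documents give no L, so a range is shown.

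- Undefined: P(B = 0) = e^(−L).
- Upward call: U = Σ over b ≥ 1 of P(B = b) × P(T ≥ 1.5b).
- Downward call: D = Σ over b ≥ 1 of P(B = b) × P(T ≤ 0.5b).
- Chance call given a defined baseline: (U + D)/(1 − e^(−L)).

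**Example, L = 2.** P(B = 0) = 0.1353. For b = 1 (probability 0.271), T ≥ 2 has probability 0.594 and T = 0 has 0.135. For b = 2 (0.271), T ≥ 3 has 0.323 and T ≤ 1 has 0.406. Summing over all b gives U = 0.2593 and D = 0.3196, so (0.2593 + 0.3196)/0.8647 = 0.67.

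**Results with no true change, and upward calls under an assumed 3-fold rise:**

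| L (cells in 10 fields) | Baseline zero | Either direction, if defined | Upward only, if defined | Upward with 3-fold rise, if defined |
|---|---|---|---|---|
| 1 | 36.8% | 70.5% | 18% | 65% |
| 2 | 13.5% | 67% | 30% | 82% |
| 3 | 5.0% | 60% | 32% | 88% |
| 5 | 0.7% | 47.5% | 29% | 93% |
| 10 | about 0 | 29% | 20% | 98% |
| 20 | about 0 | 13% | 11% | 99.8% |
| 30 | about 0 | 7% | 6.5% | about 100% |
| 50 | about 0 | 2.5% | 2.4% | about 100% |

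**Subjects with no defined outcome among 12.** 12 × e^(−L) gives 4.4 at L = 1, 1.6 at L = 2 and 0.6 at L = 3. With a 3-fold rise from L = 1, the share going from zero to positive is e^(−1) × (1 − e^(−3)) = 0.368 × 0.950 = 35%.

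**What the interval would show.** At L = 2 with no change, 12 subjects with defined baselines give 12 × 0.67 ≈ 8 expected responders. The exact 95% interval for 8/12 is 35% to 90%, which reads as activity.

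**Sensitivity.** Each biopsy is a separate 3-mm punch of a non-indicator lesion, so variation between biopsies is likely to add to the counting noise. With an assumed between-biopsy coefficient of variation of 0.5 (negative binomial, k = 4), chance calls in either direction are 74% at L = 1, 57% at L = 10, 49% at L = 50 and 47% at L = 200. Under that assumption a high count does not remove the problem.

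**The case against.** The strongest case on the other side has five parts.

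- **Baseline unknown.** No orf59 baseline is given, and category 0 belongs to a generic scale for every stain except Ki-67. This stands: the frequency of zero or low baselines is an assumption.
- **Induction concerns rises only.** Upward chance calls are 18%, 30%, 29% and 20% at means of 1, 2, 5 and 10, against 65%, 82%, 93% and 98% under a 3-fold rise. This stands, and it shows that a large induction would still shift the proportion. The rule as written, however, counts both directions.
- **Other evidence exists.** The 0/1+/2+ score registers a change from zero. For QPCR the protocol says: "Real-time QPCR based profiling of KSHV transcription will be used to test the hypothesis that depletion of VEGF directly or indirectly", and Appendix V sets out to "measure the RNA levels of all KSHV/HHV-8 mRNAs in tumor biopsies". This stands in part. QPCR measures RNA in a separate biopsy rather than orf59 protein, and section 11.2 specifies no analysis of either the score or the QPCR data.
- **A general sentence in section 11.2 offers paired t-tests of on-treatment against baseline values.** It names no variable and also refers to a baseline within each cycle, which a single pair of biopsies does not have. It cannot be relied on to cover these markers.
- **Weight.** Objective 2.2.5 names neither orf59 nor LANA, Appendix XIII calls the assay a research test, and no decision depends on it. This stands and limits the seriousness.

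A reader might infer that orf59 induction cannot be measured at all, or that zero-baseline subjects will be dropped from the denominator. The documents support neither. The counts are collected and other readouts exist, and section 11.2 refers to a proportion of patients without excluding anyone; it leaves the case unaddressed.

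**Conclusion.** The point holds as a weakness of one summary statistic. The 50%-change proportion is undefined at a zero baseline, which follows from its definition. At low counts it is unreliable: with no true change and a defined baseline, 70.5% to 47.5% of subjects would be called responders at expected totals of 1 to 5 cells, falling to 13% at 20 and 2.5% at 50. Those figures rest on independent Poisson counts and an assumed range of means. Variation between biopsies would raise them.

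As written, the proportion is not a sound measure of orf59 induction, because the zero-to-positive subject has no defined outcome. How many subjects this affects cannot be determined from the documents. The endpoint is secondary and descriptive, and the conclusions on safety, maximum tolerated dose and response rate do not depend on it. The change should be made because it is cheap and because choosing a rule after seeing the counts would weaken the result.

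**What to change.** In section 11.2, for each of the eight markers:

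1. Add the paired absolute change in index, reported as the median change with a confidence interval. Accompany it with a signed-rank test that keeps zero differences in the ranking (for example Pratt's method), labelled descriptive and unadjusted for multiplicity. The standard version discards ties, which under the no-change model are about 31% of pairs at L = 1 and 21% at L = 2.
2. Keep the 50% proportion as a supporting summary, split into rises and falls, with the number of subjects with a zero baseline shown beside it.
3. Report zero-to-positive conversion separately for orf59.
4. State the index formula, and reconcile the count index in section 11.2 with the 0/1+/2+ score in section 4.2.2.1.

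The cost is SAP wording and a little programming, with no new samples. The analysis becomes slightly longer, and the 50% proportion is reported on fewer subjects.
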